### 5.7 Prior and Concomitant Therapy

To reduce the risk of intraocular inflammation, participants may be placed on prophylactic steroids prior to the study agent administration as described in the Study Manual of Procedures.

Potential participants who are taking a carbonic anhydrase inhibitor can be recruited for enrollment in this study but they will be required to discontinue this treatment at least 3 months prior to receiving study agent in order to meet the eligibility criteria.

Participants in all groups will be advised not to take any carbonic anhydrase inhibitor medication during the 6 months after study agent administration. At the Month 6 visit, the investigator may discuss potential use of carbonic anhydrase inhibitor with the subject. Short term carbonic anhydrase inhibitor use to treat IOP spikes after intravitreal study agent administration is allowed.

Participants will be instructed to discontinue aspirin, aspirin-containing products, and any other drugs that may alter coagulation, at least 7 days prior to study agent administration. Participants will be told they may resume taking these types of products starting the day after study agent administration.

Elevated intraocular pressure will be treated using standard methods at the discretion of the investigator.

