# 1 BACKGROUND INFORMATION AND SCIENTIFIC RATIONALE

### **1.1 Background Information**

### 1.1.1 X-linked Retinoschisis

X-linked retinoschisis (XLRS), also known as X-linked juvenile retinoschisis, is an early onset retinal degenerative disease and is the leading cause of juvenile macular degeneration in males. Characteristic features include mild to severe loss in central vision, radial streaks arising from foveal schisis, splitting of inner retinal layers in the peripheral retina, and a negative electroretinogram (ERG) arising from a marked reduction in b-wave amplitude [1, 2]. Best corrected visual acuity is reduced to 20/100 or worse in most patients [3]. Disease progression and severity is highly variable even within families. During the course of the disease, secondary complications including retinal detachment and vitreous hemorrhage can occur, leading to a poor outcome. Female carriers are asymptomatic although detailed clinical examination can reveal minor retinal abnormalities [4].

XLRS is caused by mutations in the gene that encodes a protein called retinoschisin (RS1), a cell-surface adhesion molecule expressed by photoreceptor and bipolar cells of the retina [3]. The 24-kDa protein has two conserved sequence motifs; an initial signal sequence targets the protein for secretion and the larger discoidin domain is implicated in cell adhesion. RS1 helps to maintain the structural organization of the retinal cell layers and promotes visual signal transduction.

There is no specific treatment for XLRS. Anecdotal reports suggest that topical carbonic anhydrase inhibitors may provide some reduction in degree of schisis detected by OCT and improvement in visual acuity in some but not all patients [5-9], but the absence of controlled clinical trials makes interpretation of these reports difficult. No products have been approved by regulatory agencies for treatment of this condition.

Mice deficient in retinoschisin have been developed and used to obtain insight into the role of retinoschisin in retinal structure, function and pathology. Studies in these murine models of XLRS have shown that recombinant adeno-associated virus (rAAV) gene therapy vectors expressing normal RS1 can provide significant restoration of retinal structure and function in RS1-deficient mice [10-16]. These studies support the medical plausibility that intraocular delivery of a rAAV vector expressing human RS1 in patients with XLRS will also provide benefit to these patients.

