### 6.3 Medical History and Physical Examination

A medical history will be obtained, including demographic information (date of birth, gender, race and ethnic background), at the screening visit.

A complete physical examination will be performed at the screening or baseline visit, to include vital signs (oral temperature, heart rate, respiratory rate and blood pressure), height, weight and examination of major organ systems (head/eyes/ears/nose/throat, neck, cardiovascular, respiratory, abdomen, musculoskeletal/extremities, skin, lymph nodes and neurological).

A clinical evaluation, consisting of an interim medical history, including use of carbonic anhydrase inhibitors and other medications, a review of AEs and a symptom-directed physical examination, will be obtained at all other visits.

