# 6.12 Optical Coherence Tomography

Retinal anatomy will be evaluated by spectral domain optical coherence tomography (SD-OCT) scans of both eyes once at the screening visit, twice at the baseline visit, and once at visits 1, 2, 3, 6, 9 and 12 months after study agent administration. Additional SD-OCT scans may be obtained at the discretion of the investigator. Each SD-OCT will generate macula volume scans and high resolution horizontal and vertical scans centered on the fovea.

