# **10.2 Study Population**

Approximately 27 male individuals with XLRS will be enrolled in this study.

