14 July 2017	6.0	Revised estimated study enrollment duration in the Protocol Summary and Section 3.
		Revised estimated number of participants in the Protocol Summary and Sections 3, 4, and 10.2.
		Modified the study design to include Group 2A throughout the protocol. Participants in this group will be 6-17 years old and receive the study agent at the middle dose.
		Added clarifications for the MTD throughout the protocol.
		Updated section 1.3.1 to further clarify risks related to the use of steroids.
		Added risks associated with anesthesia to section 1.3.1.
		Revised Sections 4.1 and 10.3 to include the new Group 2A and to clarify the washout period for CAIs.
		Updated Exclusion Criteria # 3 (section 4.3).
		Added clarification to Section 7.2.1.5 regarding SAE definition.
		Fixed minor typographical and formatting errors.

Date	Protocol Version	Summary of Changes
12 January 2018	7.0	Added risks associated with the study in Section 1.3.1. Added "Ocular Fluids" Section 6.5. Clarification added to the Storage of Samples for Future Research in Section 13.7.
21 October 2019	8.0	Removal of efficacy testing at LTFU visits: 12 month analysis revealed that AGTC-301 is generally safe and well-tolerated, but has no evidence of a treatment effect. Addition of LTFU questionnaire in Appendix B Updated publication policy

# SITE-SPECIFIC APPENDIX 1

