4.1 General Study Design

This is a non-randomized, open-label, Phase 1/2 dose escalation study of the safety and efficacy of rAAV2tYF-CB-hRS1 administered by intravitreal injection in one eye in individuals with XLRS. The primary objective is to evaluate safety and the secondary objective is to evaluate efficacy.

Each participant is to receive rAAV2tYF-CB-hRS1 by intravitreal injection in one eye on a single occasion as outlined in the schematic below.

		Number of Dose Level				
Group ^a	Age (yr)	Subjects	vg/mL	Volume	vg per eye	
1A	≥ 18	3	1.43 × 10 ¹²	0.07 mL	1 × 10 ¹¹	
1B	≥ 18	3	1.43 × 10 ¹²	0.07 mL	1 × 10 ¹¹	
2	≥ 18	3	4.3 × 10 ¹²	0.07 mL	3 × 10 ¹¹	
2A	6-17	Up to 6	4.3 × 10 ¹²	0.07 mL	3 × 10 ¹¹	
3	≥ 18	3	4.3 × 10 ¹²	0.14 mL	6 × 10 ¹¹	
4	≥ 6	Up to 15	MTD ^b	MTD	MTD	

Schematic of Study Design:

^a Visual acuity not better than 58 Early Treatment Diabetic Retinopathy Study (ETDRS) letter score in Group 1A, 63 in Groups 1B, 2, 2A & 3, 68 in Group 4.

^b MTD = maximum tolerated dose determined in Groups 1A, 1B, 2 and 3 for adults, in Groups 1A, 1B, 2, and 3 (adult participants only) and 2A (pediatric participants only) for pediatric participants.

Participants in Groups 1A, 1B, 2 and 3 are at least 18 years of age and receive the vector at a lower dose (Groups 1A and 1B), middle dose (Group 2) or higher dose (Group 3). Participants in Group 1A have visual acuity that is worse than participants in subsequent groups (ETDRS letter score of 58 in Group 1A and 68 in other groups). Participants in Group 2A will be 6-17 years of age and receive the

vector at the middle dose level. Participants in Group 4 will be at least 6 years of age and will receive the vector at the maximum tolerated dose (MTD) determined in Groups 1A, 1B, 2, and 3 for adults; in Groups 1A, 1B, 2, and 3 (adult participants only) and 2A (pediatric participants only) for pediatric participants.

Participants in all groups are selected from individuals who are not being treated with a carbonic anhydrase inhibitor during the study and have not been treated with any carbonic anhydrase inhibitor within the 3 months prior to enrollment in the study. Participants are asked not to begin treatment with a carbonic anhydrase inhibitor within 6 months after study agent administration.

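### Does the SAP need a rule for acuity and OCT values taken after a participant starts a carbonic anhydrase inhibitor?

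*Protocol*

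**What the plan says.** Protocol 5.7 limits its advice in time: "Participants in all groups will be advised not to take any carbonic anhydrase inhibitor medication during the 6 months after study agent administration". It then adds "At the Month 6 visit, the investigator may discuss potential use of carbonic anhydrase inhibitor with the subject", and it separately allows short-term use for pressure spikes after the injection. No restriction is stated after Month 6.

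The reason these drugs matter is in Protocol 1.1.1, which cites anecdotal reports on topical CAIs in these words: "anhydrase inhibitors may provide some reduction in degree of schisis detected by OCT and improvement in visual acuity in some but not all patients". The same sentence warns that the absence of controlled trials makes those reports hard to interpret.

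OCT is done "once at visits 1, 2, 3, 6, 9 and 12 months after study agent administration" (Protocol 6.12). Acuity is measured at every visit after dosing, through Year 5 (Protocol 6.10). SAP 15.1 and 15.2 apply paired t-tests of post-baseline visits against baseline for both. They add a study-eye versus fellow-eye test for acuity and, among the OCT measures, for cystic cavity volume only. SAP 15.1 labels all inferential statistics exploratory.

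On the medication data, the interim history at each visit after screening records matters "including use of carbonic anhydrase inhibitors and other medications" (Protocol 6.3). SAP 12.2 treats CAIs as concomitant medication, tabulates concomitant medication by group and drug class (Table 14.1.5), and gives CAI use its own listing (16.2.4.5.2). The per-protocol set in SAP 8 is optional and removes users of prohibited medication; a CAI begun after Month 6 is not prohibited.

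SAP 4.1 describes participants as "not being treated with a carbonic anhydrase inhibitor during the study", but its next sentence gives the 6-month limit.

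**The concern.** The baseline is free of CAIs by design, while Months 9 and 12, and acuity in Years 2 to 5, need not be. There is no untreated arm. A participant who starts a CAI after Month 6 and improves because of it would add to the mean change attributed to the vector. Nothing in SAP 15.1 or 15.2 flags, excludes or models those values, and the medication table is split neither by visit nor against efficacy results. A reader of the efficacy tables alone would not see that Month 12 differs from Month 6 in this respect, and the loose phrase in SAP 4.1 could suggest that the whole study is CAI-free. At stake is a false impression of benefit in acuity or schisis at the later visits.

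**Working it through.** **Inputs.** The only relevant figure in the documents is the sample size: "Approximately 27 male individuals with XLRS will be enrolled in this study" (Protocol 10.2). They give no CAI uptake, CAI effect or SD of change, so there is no plan figure on this point to reproduce, and everything below is illustrative. Assumptions: uptake u = 30%, effect e = 5 letters, no vector effect, SD of change S from 6 to 12 letters. Analysed groups assume enrolment of 3+3+3+6+3+9 = 27 with Group 2A full, so Group 4 has 9, Groups 3+4 have 12, Groups 2+2A have 9 and Group 2A has 6.

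**Bias and paired test.** Bias = u × e = 0.3 × 5 = 1.5 letters. SD of the observed change = √(S² + u(1−u)e²). Noncentrality = bias × √n / SD, with rejection from the noncentral t at two-sided 5% and n−1 degrees of freedom.

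- S = 6, n = 27: SD = √(36 + 5.25) = 6.42; noncentrality = 1.5 × √27 / 6.42 = 1.21; rejection 21.5%.
- S = 12, n = 27: SD = √(144 + 5.25) = 12.22; noncentrality 0.64; rejection 9.4%.

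| Group | n | Rejection, S = 12 to S = 6 |
|---|---|---|
| All subjects | 27 | 9.4% to 21.5% |
| 3+4 | 12 | 6.8% to 11.5% |
| 4, or 2+2A | 9 | 6.2% to 9.5% |
| 2A | 6 | 5.7% to 7.6% |

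At 10% uptake and 3 letters, the bias is 0.1 × 3 = 0.3 letters, and rejection at n = 27 is 5.2% to 5.7%.

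**Fellow-eye test.** This was simulated as a pooled two-sample t-test on change, with u = 30%, e = 5, n = 27 and between-eye correlation of change 0 or 0.5 (assumed). If both eyes share the CAI effect, rejection is about 0.4% to 5%, so there is no inflation. If only the study eye has it, rejection is about 2% to 14%.

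**What omission would do.** Setting aside values after CAI start removes about 0.3 × 27 ≈ 8 participants. The standard error rises by √(27/19) = 1.19, or 19%. If those who start are the worst 8 of 27 at Month 6 (S = 8, simulated), the mean at Month 12 rises with no treatment effect at all:

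| Month 6 to 12 correlation (assumed) | Shift in mean, letters |
|---|---|
| 0.3 | +1.1 |
| 0.5 | +1.9 |
| 0.7 | +2.7 |

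The shift runs in the same direction as the 1.5-letter CAI bias and exceeds it for correlations of 0.5 and 0.7.

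**What the plan already does.** SAP 8 analyses all injected subjects, SAP 9.2 leaves missing values missing, and SAP 15.1 and 15.2 use each scheduled value. Together these amount to an as-observed analysis. Months 1, 2, 3 and 6 are tested separately and are CAI-free by plan, apart from short-term use for pressure spikes. With about 27 participants and all data listed by group, subject and visit (SAP 9.4), CAI use can be matched to each value by eye.

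**The case for a change.** The strongest case for acting is that the protocol itself names acuity and schisis as outcomes a CAI may alter, and that no provision ties CAI use to those outcomes. The per-protocol set does not reach permitted use, and the medication table does not separate visits. Acuity also continues to Year 5, when use can accumulate. A sentence naming Month 6 as the last planned CAI-free efficacy visit and a count of users at Months 9 and 12 would cost almost nothing.

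All of that is accurate. The sentence and the count would help a reader, and a careful analyst may well add them when reporting, but they alter no estimate or test. The only proposal that would produce different numbers is the analysis omitting post-CAI values, and it is not shown to be better than what it would check.

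It could also be argued that macular volume and the thickness segments are the exposed measures, because they have only the paired test. Protocol 1.1.1 speaks only of schisis and acuity. A CAI effect on those other measures is an inference the documents do not state. The SAP's direct measure of schisis, cystic cavity volume, does have the fellow-eye comparison.

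**Conclusion.** The gap is real, but it does not call for a change. The SAP does not say how values after CAI start are handled; its default is to analyse them as observed, which is a fair choice for exploratory tests in a small open-label study with safety as the primary objective. The illustrated bias is 1.5 letters at 30% uptake and 5 letters, and 0.3 letters at 10% and 3 letters. Both rest wholly on assumed inputs. The alternative of omitting values trades that for a possible selection shift of 1.1 to 2.7 letters and a 19% larger standard error.

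The direction of the bias matters too. CAI use of the kind described would make change from baseline look better, whereas the version 8.0 entry in Protocol Appendix C states "12 month analysis revealed that AGTC-301 is generally safe and well-tolerated, but has no evidence of a treatment effect". That version also removed efficacy testing other than acuity from the long-term visits, which leaves little at risk after Month 12.

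The phrase in SAP 4.1 about CAI use during the study is a clerical slip. It does not match the 6-month limit in its own next sentence and in Protocol 5.7, and the wording can be reconciled whenever the SAP is next opened.

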## 5.8 Accountability Procedures for the Study Agent

Study agent will be dispatched to the site after receipt of required documents in accordance with applicable regulatory requirements and AGTC procedures.

Study agent must be administered according to procedures described herein. Only subjects enrolled in the study may receive study product, in accordance with all applicable regulatory requirements. Only authorized site personnel may administer study agent. Study agents must be stored in a secure temperature-controlled area with access limited to the investigator and authorized study site personnel.

The investigator is responsible for study agent accountability, reconciliation and record maintenance. In accordance with all applicable regulatory requirements, the investigator or designated study site personnel must maintain study agent accountability records throughout the course of the study. This will include documentation of the amount of study agent received from AGTC and the amount administered to study participants.

# 6 STUDY PROCEDURES/EVALUATIONS

Study agent administration will occur on Day 0. There will be a screening visit that will occur within 3 months prior to study agent administration and a baseline visit that will occur within 7 days prior to study agent administration. There will be an additional 10 visits (including Day 0) during the first year of this study and annual long-term follow-up visits during the subsequent 4 years.

Individuals who have been participating in the natural history study XLRS-001, entitled "Clinical Evaluation of Individuals with X-linked Retinoschisis (XLRS)", may discontinue their participation in that study and be enrolled in the present study if all appropriate entry criteria are met. In this case, results of the evaluations from the most recent visit in the natural history study, excluding OCT, can be used as part of the appropriate screening visit evaluations for the present study, as long as all the evaluations were conducted per the current Study Manual of Procedures and Reading Center Manual of Procedures and the visit occurred no more than 3 months prior to the planned date of study agent administration. If the most recent visit occurred more than 3 months prior to the planned date of study agent administration, all screening visit examinations will be performed.

A Time and Events Schedule of study procedures and evaluations is provided in Appendix A. The windows for the timing of the study visits are provided in the Study Manual of Procedures.

## 6.1 Informed Consent/Assent

Potential participants (and a parent or guardian of children <18 years of age) will be invited to provide written informed consent (and assent from children <18 years of age) prior to any screening evaluations. An investigator or study coordinator will provide a full explanation of the study, including potential risks of participation and that they may withdraw from the study at any time and for any reason without jeopardizing their future treatment, and an investigator will provide answers to all questions raised by the potential participant (and a parent or guardian of children <18 years of age). After ensuring that all questions have been answered, written documentation of the informed consent/assent decision will be obtained.

No study-related procedures will be performed until after informed consent/assent is obtained.

A list will be maintained of all potential participants who participate in screening that will include the person's initials, the date of screening, the outcome of screening (i.e. eligible or not eligible) and, for persons who do not enroll in the study, the reason for non-enrollment.

## 6.2 DNA Testing

If a potential participant has not previously had a mutation in the RS1 gene documented by genetic testing, a blood or saliva sample will be obtained for genetic testing to confirm the subject has a mutation in the RS1 gene.

### 6.3 Medical History and Physical Examination

A medical history will be obtained, including demographic information (date of birth, gender, race and ethnic background), at the screening visit.

A complete physical examination will be performed at the screening or baseline visit, to include vital signs (oral temperature, heart rate, respiratory rate and blood pressure), height, weight and examination of major organ systems (head/eyes/ears/nose/throat, neck, cardiovascular, respiratory, abdomen, musculoskeletal/extremities, skin, lymph nodes and neurological).

A clinical evaluation, consisting of an interim medical history, including use of carbonic anhydrase inhibitors and other medications, a review of AEs and a symptom-directed physical examination, will be obtained at all other visits.

### 6.4 Hematology and Clinical Chemistries

Hematology and clinical chemistry will be obtained at the screening or baseline visit and at visits 7 and 14 days after study agent administration. Hematology will include hemoglobin, hematocrit, white blood cell count and platelet count. Clinical chemistry will include sodium, potassium, chloride, total protein, albumin, calcium, phosphorous, glucose, blood urea nitrogen, creatinine, total bilirubin, alkaline phosphatase, lactate dehydrogenase, aspartate aminotransferase and alanine aminotransferase.

### 6.5 Ocular Fluids

Ocular fluids collected during procedures may be stored and used for future analyses.

### 6.6 Coagulation

Coagulation tests (prothrombin time and partial thromboplastin time) will be obtained at the screening or baseline visit.

### 6.7 Immunology

Serum to measure antibodies to AAV will be obtained at the screening visit and at visits 1, 3, 6 and 12 months after study agent administration. Serum to measure antibodies to RS1 will be collected at the baseline visit, at visits 1, 3 and 12 months after study agent administration.

Peripheral blood mononuclear cells (PBMC) will be collected at the baseline visit and at visits 1, 2 and 3 months after study agent administration. Aliquots of these PBMC samples will be stored for possible future analyses including measurement of T cell responses to AAV or RS1.

### 6.8 Vector Analysis

Whole blood for detection of vector DNA by polymerase chain reaction (PCR) assay will be obtained at the baseline visit and at visits 1, 7 and 14 days after study agent administration.

### 6.9 **Ophthalmic Examinations**

Ophthalmic examinations of both eyes will be performed at the screening and baseline visits and at each visit after study agent administration, including each long-term follow-up visit. These examinations will include slit lamp examination, tonometry, indirect ophthalmoscopy and retinal biomicroscopy. Signs of inflammatory responses will be quantified using a standard 0 to 4+ cells and flare grading system [59]. On the visit at which the study agent is administered, IOP in the study eye will be measured about 30 minutes after study agent administration is completed.

# 6.10 Visual Function Measurements

All visual function measurements will be obtained for both eyes at each visit when such testing is performed.

Best corrected visual acuity (BCVA) testing will be performed once at the screening visit, twice at the baseline visit, and once at each visit after study agent administration, including each longterm follow-up visit. BCVA will be determined using a standard Early Treatment of Diabetic Retinopathy Study (ETDRS) visual acuity testing protocol.

Visual field and microperimetry testing will be performed once at the screening visit, twice at the baseline visit, once at visits 1, 2, 3, 6, 9, and 12 months after study agent administration. Visual field testing will be performed using the Haag Streit Octopus 900 perimeter. Static perimetry will use the German Adaptive Thresholding Estimation (GATE) method and kinetic perimetry will use the Semi-automated Kinetic Perimetry (SKP) method. Microperimetry will be performed using the MP1 microperimeter.

Reading speed and contrast sensitivity testing will be performed once at the screening visit, twice at the baseline visit, and once at visits 3, 6, 9, and 12 months after study agent administration. Reading speed will be measured using MNREAD charts. Contrast sensitivity will be measured using Pelli-Robson charts.

Additional non-invasive measures of visual function may also be performed at the discretion of the investigator.

